6.7.3. Transfusion Frequency as an Exploratory Efficacy Endpoint

Summaries will be provided for RBC and platelet transfusions separately. The number and percent of subjects who received transfusions from the date of randomization to 30 days after the last dose will be summarized by treatment arm. The total number of units transfused per subject, and exposure-adjusted transfusion rate will be summarized for each transfusion category by treatment arm. An exposure-adjusted transfusion rate (units per patient-month) is defined as (total number of units across all subjects) / (total patient-months across all subjects), where for each subject, patient-months is defined as [(last dose date + 30) – (randomization date) + 1] / 30.4375.

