Vital signs	Temperature, blood pressure (BP) and heart rate (HR) will be assessed prior to each study treatment dosing 
 On talacotuzumab dosing days BP/HR are measured pre-dose and every 15 min during the first 90 min, and then at 30-min intervals for the remainder of the infusion. For the first infusion, obtain every 30 min post-infusion up to 1.5 hr after the infusion 	X	X	X	

Procedure (Part B)	Notes	Screening Phase	Open-Label Treatment Phase		Follow-up Phase
		Within 28 days before randomization	Day 1 of each cycle (\pm 48 hours) unless otherwise indicated (each cycle = 28 days)	EOT	Every 3 months (\pm 7 days)
Weight	Must be assessed within 3 days prior to dosing on Day 1 of each specified cycle, in case of weight loss of >10% within a cycle, the dose of study drug must be recalculated	X	X	X	
Height		X			
LVEF	MUGA scan is preferred. Echocardiogram can be used if MUGA is not available.	X	as clinically indicated	X	
ECG	QTcF will be assessed at the time of screening. If QTcF is >470 msec, repeat ECG 2 additional times approximately 3 – 5 minutes apart. Average the QTcF of all 3 ECGs to determine if the subject meets the QTc eligibility criteria	X	For subjects in Arm 1, ECG monitoring will occur on Cycle 1 Day 8 and Day 22 after the talacotuzumab IV infusion, then every other cycle thereafter on Day 22 after the talacotuzumab IV infusion. For subjects in Arm 2, ECG monitoring will occur on Cycle 1 Day 5 after the decitabine IV infusion and then every 2 cycles thereafter on Day 5 after the decitabine IV infusion.	X	
Concomitant medications	See Section 8 for detailed instructions; Includes transfusion requirements	Continuous from the time of signing of ICF until 30 days after last study drug dose			Concomitant medications for related AEs of Grade \geq 3 and SAEs regardless of relationship; subsequent anticancer therapy

Procedure (Part B)	Notes	Screening Phase	Open-Label Treatment Phase		Follow-up Phase
		Within 28 days before randomization	Day 1 of each cycle (\pm 48 hours) unless otherwise indicated (each cycle = 28 days)	EOT	Every 3 months (\pm 7 days)
Adverse events	See Section 12 for detailed instructions.	Continuous from the time of signing of ICF until 30 days after last dose of last study drug			Related AEs of Grade \geq 3 and related SAEs; follow until resolution

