Abbreviations: AE=adverse event; ALT= alanine aminotransferase; AML=acute myeloid leukemia; ANC= absolute neutrophil count; AST= aspartate aminotransferase; β -hCG=beta human chorionic gonadotropin; CCO=clinical cut-off; CR= complete response; CRi= complete response with incomplete blood count recovery; BP=blood pressure; BUN= blood urea nitrogen; ECG=electrocardiogram; ECOG=Eastern Cooperative Oncology Group; EOT=end of treatment; EQ=EuroQol; HBV: hepatitis B virus; HR=heart rate; ICF=informed consent form; INR= international normalized ratio; LDH= lactate dehydrogenase; LVEF= left ventricular ejection fraction; MRD= minimal residual disease; MUGA= multi gated acquisition scan; NK= natural killer (cells); PD=pharmacodynamics(s); PK=pharmacokinetic(s); PT= prothrombin time; aPTT= partial thromboplastin time; SAE=serious adverse event; T&E=Time & Events; WBC= white blood cell.					

TIME AND EVENTS SCHEDULE – TABLE 1C [PART B] DURING AMENDMENT 6

Procedure (Part B)	Notes	Screening Phase	Open-Label Treatment Phase		Follow-up Phase
		Within 28 days before randomization	Day 1 of each cycle (\pm 48 hours) unless otherwise indicated (each cycle = 28 days)	EOT	Every 2 months (\pm 7 days)
NOTE Following Amendment 6, which incorporated the IDMC's recommendations to close enrollment to the study and discontinue talacotuzumab treatment for subjects receiving talacotuzumab + decitabine and offer to continue decitabine alone, all subjects will continue to be followed for survival and subsequent anti-cancer therapy. During the treatment phase with decitabine, subjects will be monitored for serious adverse events.					
Serious adverse events	Follow until resolution		X		
Survival, subsequent therapy			X	X	X
EOT= end-of-Treatment; IDMC= Independent Data Monitoring Committee					

TIME AND EVENTS SCHEDULE – TABLE 1D [PART B] FOLLOWING AMENDMENT 7

Procedure (Part B)	
NOTE Following Amendment 7 and when 270 deaths have occurred or 6 months after the last subject is enrolled (whichever occurs first), follow up of subjects and data collection will end. Subjects who are continuing to derive benefit from decitabine treatment as assessed by their investigator may continue to receive decitabine; during this period, only serious adverse events will be monitored and entered into the Company safety repository.	

TIME AND EVENTS SCHEDULE (PK AND BIOMARKERS) – TABLE 2A [PART A]

PART A	Cycle 1						Cycle 2	Cycles 3 and 5	EOT ¹
	Talacotuzumab alone						Decitabine + Talacotuzumab		

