6.1.2. Part B

In Part B of the study, subjects will receive study therapy according to the arm to which they are assigned. The start of each cycle is defined as the date of the first dose of decitabine. Cycles may be delayed due to recovery from toxicity or other causes. Study treatment continues until treatment failure, relapse from CR/CRi, unacceptable toxicity, death, or other reasons specified in Section 10.2.

In Arm 1, study therapy Cycle 1 will start with decitabine at a dose of 20 mg/m² IV administered daily for five consecutive days followed by IV treatment with talacotuzumab (at the RP2D) on Days 8 and 22 (\pm 24 hours) of a 28-day cycle. Subsequent cycles of study therapy will follow the same dosing schedule as Cycle 1 as outlined in Table 3.

Table 3: Dosing Schedule for Part B - Arm 1

Study Day	All treatment cycles									
	1	2	3	4	5	6-7	8	9-21	22	23-28
Decitabine (20 mg/m ²)	X	X	X	X	X					
Talacotuzumab (RP2D mg/kg)							X		X	

Subjects assigned to Arm 2 will receive decitabine at a dose of 20 mg/m² IV administered daily for five consecutive days. A Cycle of study therapy will be repeated every 28 days from the first dose of decitabine onwards. The dosing schedule for Arm 2 is outlined in Table 4.

Table 4: Dosing Schedule for Part B - Arm 2

Study Day	All treatment cycles					
	1	2	3	4	5	6-28
Decitabine (20 mg/m ²)	X	X	X	X	X	

Investigators should be aware that for treatment with decitabine as monotherapy or in combination, it is recommended that subjects be treated for a minimum of 4 cycles; however, a complete or partial response may take longer than 4 cycles.

Study treatment is to continue until treatment failure, relapse from CR/CRi, or death, unless discontinued early because of unacceptable toxicity. Subjects in Arm 1 may discontinue 1 of the study treatments (decitabine or talacotuzumab) because of unacceptable toxicity and continue treatment the other agent until treatment failure, relapse from CR/CRi, or death, unless discontinued early because of unacceptable toxicity.

Following Amendment 6, enrollment to the study was closed and subjects receiving talacotuzumab + decitabine should discontinue talacotuzumab treatment and may continue to receive decitabine alone, according to Principal Investigator decision and subject agreement.

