5.4. Convention of Time Computations

By convention, one month equals to 30.4375 days and one year equals to 365.25 days. Duration in days between 2 time points will be calculated as (end date – start date + 1).

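### The transfusion-rate denominator in SAP 6.7.3 runs to last dose + 30 days even after death, loss to follow-up or clinical cutoff, so the rate is understated, probably by a small amount

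*SAP*

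**What the plan says.** SAP 6.7.3 defines the exposure-adjusted transfusion rate, for red cells and platelets separately and by arm, as ("total number of units across all subjects) / (total patient-months across all subjects"). Each subject's patient-months come from "last dose date + 30) – (randomization date) + 1] / 30.4375". The number and percent of subjects transfused are counted "from the date of randomization to 30 days after the last dose". No window is stated for units, but the same one is implied.

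Other places that bear on this:

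- Protocol 6.1.2: "Study treatment is to continue until treatment failure, relapse from CR/CRi, or death", unless toxicity intervenes. Death soon after a dose is therefore an expected path.
- SAP Section 3, last paragraph: the analyses use data up to a cutoff 6 months after the last randomization. Protocol Section 7 closes the eCRFs at the end of data collection.
- Protocol Table 1B (up to Amendment 5) captures transfusions in the concomitant-medications row: "See Section 8 for detailed instructions; Includes transfusion requirements".
- Protocol Table 1C (during Amendment 6) has two rows, one for serious adverse events and one for survival and subsequent therapy. Its note says "During the treatment phase with decitabine, subjects will be monitored for serious adverse events". The opening of Protocol Section 9 repeats this.
- Protocol Section 8 still requires concomitant therapies to be recorded up to 30 days after the last dose.

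**The concern.** A rate per patient-month is interpretable only if numerator and denominator cover the same time at risk. A subject who dies ten days after the last dose can contribute no units for the other twenty days, yet the formula credits all thirty. The same holds for a subject lost to follow-up inside the 30 days, and for a subject still being dosed within 30 days of cutoff, because data after cutoff are not analysed. Every such error adds time and no units, so the bias has one direction: the rate is too low.

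Last dose + 30 days is a sensible window for counting events, because a dead subject simply has none. It becomes wrong when it is reused as person-time. SAP 5.15 ends the adverse-event window at the earlier of two dates; 6.7.3 has no earlier-of rule.

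Amendment 6 raises a related question. Decitabine could continue, so last-dose dates can fall after the amendment. If transfusions were no longer recorded then, the denominator would grow while the numerator stood still. At stake is a by-arm summary of the one exploratory endpoint that SAP 2.2 names for the clinical study report.

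**Working it through.** The documents state no transfusion rate, so there is no figure to reproduce. The month constant is consistent with SAP 5.4: 365.25 / 12 = 30.4375.

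**One subject (assumed dates and units).** Randomized day 1, last dose day 61, 6 units, death on day 71.

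- SAP formula: (61 + 30) - 1 + 1 = 91 days; 91 / 30.4375 = 2.990 months; 6 / 2.990 = 2.01 units per month.
- Stopped at death: 71 / 30.4375 = 2.333 months; 6 / 2.333 = 2.57 units per month.
- Relative error: 71/91 - 1 = -22%. It ranges from -33% for death on the last-dose day (61/91 - 1) to 0% for death 30 days after it.

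**Arm level, deaths only.** Let L be the mean days from randomization to last dose and q the share dying within 30 days of it, uniformly, so that 15 excess days are counted on average. Understatement = 15q / (L + 30). L and q are assumed.

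| L (days) | q = 0.10 | q = 0.25 | q = 0.50 |
|---|---|---|---|
| 60 | 1.7% | 4.2% | 8.3% |
| 120 | 1.0% | 2.5% | 5.0% |
| 180 | 0.7% | 1.8% | 3.6% |
| 240 | 0.6% | 1.4% | 2.8% |

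A simulation with uniform accrual over 15-25 months, exponential treatment duration with median 4-8 months, and 20-40% of those stopping dying within 30 days gives 0.8-3.0% for deaths alone. The cutoff part is not sized separately here; it is at most 30 days for each subject still on treatment at cutoff.

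**Excess days per death, by arm.** Take a death on a uniformly chosen day d of a fully dosed 28-day cycle, before Amendment 6. Excess days = (last dose day so far) + 30 - d.

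- Arm 2 (doses Days 1-5): days 1-5 sum to 150 and days 6-28 sum to 414. Mean = 564 / 28 = 20.1 days.
- Arm 1 (doses Days 1-5, 8, 22): days 1-5 sum to 150, days 6-7 to 57, days 8-21 to 329 and days 22-28 to 189. Mean = 725 / 28 = 25.9 days.

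**Amendment 6, conditional.** If a share w of counted person-time falls after transfusion recording stopped, and the true rate is constant, the understatement from this source is w. In the simulation, ending time at death, cutoff and an assumed stop of recording gives these totals (deaths and cutoff included):

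- stop 0-1 month after the last randomization: 14.7-37.6%;
- stop 2-3 months after it: about 9-25%.

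If recording continued under Section 8, this part is zero and only the death, last-contact and cutoff parts remain.

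**The case against.** The best defence concerns Amendment 6. A reader might infer from Table 1C that transfusion collection stopped and that the rate is therefore understated by 15% or more. The documents do not establish this:

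- The Table 1B row sends the reader to Section 8, whose recording period ends where the SAP window ends. Amendment 7 revised Section 8 and left that rule in place.
- Table 1C also has no study-drug row. If it is exhaustive, post-amendment dosing dates are not scheduled either. If dosing dates survive through the general text of Section 7, transfusions survive equally through Section 8.
- SAP 5.2 and 5.10 say that central review and MRD assessment ceased. The SAP says nothing similar about transfusions.
- An almost immediate stop is hard to square with Protocol 17.1, which requires ethics approval before an amendment is implemented, except for immediate hazards. The 38% end also needs a median treatment duration of 8 months, equal to the planning median for control-arm survival.

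These arguments stand. What the documents show is a conflict between Table 1C and Section 8, not a proven loss of data.

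It is also fair to say that the endpoint is exploratory and untested, that the number and percent transfused and the units per subject do not use this denominator, and that equal proportional errors cancel in a rate ratio. These arguments limit the importance of the point. None of them answers the missing stop at death, last contact and cutoff.

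**Conclusion.** The formula is wrong as written, and the direction is certain: it counts time in which no units can be recorded, so the rate is understated. For deaths alone the size is about 1-3% under the simulation's assumptions and 0.6-8.3% under the wider grid. All durations and early-death shares are assumed.

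The Amendment 6 part is conditional. It is zero if Section 8 was followed. If recording stopped, the total is about 9-38%, depending on the assumed stop date and treatment duration.

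A reader might also infer from the dosing schedules that the error favours the combination arm. The excess per death may well be larger in Arm 1 (25.9 versus 20.1 days on full dosing before Amendment 6). A net arm difference would also depend on how many subjects die soon after a dose in each arm and how long each arm is treated, which the documents do not give. It is not established.

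Severity is minor: the endpoint is exploratory and descriptive, and the CR and OS analyses are unaffected.

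**What to change.** In SAP 6.7.3, end each subject's patient-months at the earliest of last dose + 30 days, death, withdrawal or last contact, and clinical cutoff. State that units are counted over exactly the same window. Say how randomized subjects who were never dosed are handled, since they have no last-dose date.

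Reconcile Protocol Table 1C with Section 8 and record in the SAP whether transfusions were collected after Amendment 6. If they were not, also end both time and units at one common date, such as implementation of Amendment 6. A common date avoids relying on a site-level stop date, which the documents do not define as collected.

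The cost is one revised formula and one clarifying sentence, using dates the trial already holds. A little less patient time contributes, and more would be lost only if the Amendment 6 cap applies.

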6.8. Safety

6.8.1. Adverse Events

Adverse events are coded to SOC and PT terms using the Medical Dictionary for Regulatory Activities (MedDRA) coding system version 18.0 or higher.

Severity of AEs will be graded on a scale of 1 to 5 according to the NCI Common Terminology Criteria for Adverse Events (NCI CTCAE version 4.0 or higher). Adverse events will be summarized by grade according to the worst grade experienced.

Adverse events will be categorized and summarized according to their highest (worst) relationship to study medication.

Summaries of treatment-emergent AEs will be provided as incidence tables (number of subjects experiencing an event) by treatment group, by SOC and PT, by NCI toxicity grade, by relationship to study drug, and by action taken. Tables will be sorted by frequency in incidence (the highest to lowest incidence). The same summary will be provided for serious AEs, drug-related serious AEs, AEs leading to treatment discontinuation, and AEs leading to death.

For adverse events that are identified as special interest per Section 6.17, terms selected from standardized MedDRA queries (SMQs) and/or customized AE groupings that represent the clinical syndrome will be summarized. AEs of special interest, including infusion-related reactions, will be summarized by toxicity grade.

The number and percent of subjects who die during the study and cause of death will be summarized by treatment arm.

6.8.2. Clinical Laboratory Tests

Selected hematologic and chemistry laboratory parameters will be descriptively summarized at each scheduled on-treatment evaluation by treatment group. Change from baseline will also be summarized. Mean value over time will be presented graphically.

A summary of the shifts in selected laboratory hematology and serum chemistry parameters from baseline to the worst toxicity grade during the study (from treatment start to 30 days after last dose or the end of treatment visit date, whichever is later) will be provided.

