8.3. Subsequent Antineoplastic Therapies

Administration of any other antineoplastic therapy, for reasons other than treatment failure (defined in Section 9.2.1.1) or relapse from CR/CRi, is strongly discouraged until treatment

failure or relapse is established. After treatment failure or relapse is established, subsequent therapy is permitted at the investigator's discretion. Subsequent therapy (including start date, end date, and best response) should be documented in the appropriate section of the eCRF.

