9.1.3. Open-Label Treatment Phase

Details of the procedures performed during the Treatment Phase are outlined in the [Time and Events Schedule Tables 1A](#), [1B](#), and [1C](#). For Part A, treatment will start on Day 1 with an IV infusion of talacotuzumab and proceed as described in [Section 6.1](#). Subjects will continue on study and receive open label talacotuzumab in combination with decitabine in Part A until treatment failure, relapse from CR/CRi, unacceptable toxicity, death or other reasons specified in [Section 10.2](#).

For Part B, treatment with study drug should start within 3 days after randomization and continue until treatment failure, relapse from CR/CRi, unacceptable toxicity, death, or other reasons specified in [Section 10.2](#).

All subjects in Part A and Part B will be closely monitored for adverse events, laboratory abnormalities, and disease status. Clinical evaluations and laboratory studies may be repeated more frequently, if clinically indicated. If treatment failure or relapse from CR/CRi occurs, then the subject will complete the End-of-Treatment Visit and enter the Follow-up Phase. Subjects randomized into the decitabine + talacotuzumab arm can discontinue 1 drug (decitabine or talacotuzumab); while continuing treatment with the other drug.

End of Treatment

All subjects should have an End-of-Treatment Visit, unless a subject withdraws consent for study participation or is lost to follow up. The End-of-Treatment Visit is to occur within 30 days (+/- 7 days) after the last dose of study drug. Every effort should be made to conduct the End-of-Treatment Visit before the subject starts subsequent treatment.

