5.3. Study Phases

Screening Phase: Before the first dose of study medication.

Treatment Phase: Between the date of first dose of study medication and the date of the last dose of study medication plus 30 days.

End of Treatment: Date of last dose of study medication plus 30 days. Assessments performed at the “end of treatment visit” will be included in this phase.

Follow-up Phase: After end of treatment until the subject’s completion or withdraw from the study or study closeout.

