5.15. Treatment-Emergent Adverse Events

Treatment-emergent AEs are defined as those that occurred after the first dose of study drug through the last dose date + 30 days or the start of a subsequent anticancer therapy, whichever occurs earlier. Adverse events that occurred any time after the first dose of study drug during the study are also considered as treatment-emergent if they are study drug-related (ie, possible, probable, or very likely related to study drug).

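### The laboratory shift window has no cut at subsequent anticancer therapy, so samples taken after a switch can raise a subject's tabulated worst grade

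*SAP*

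**What the plan says.** SAP 6.8.2 plans a summary of shifts "from baseline to the worst toxicity grade during the study" for selected haematology and chemistry parameters. The window is "from treatment start to 30 days after last dose or the end of treatment visit date, whichever is later".

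SAP 5.15 counts adverse events as treatment-emergent "through the last dose date + 30 days or the start of a subsequent anticancer therapy, whichever occurs earlier". Its next sentence reopens the window: events at any later time are "also considered as treatment-emergent if they are study drug-related". The cut therefore bites only on events not judged related.

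SAP 5.3 defines the Treatment Phase as "Between the date of first dose of study medication and the date of the last dose of study medication plus 30 days", again with no cut at a new therapy, and places assessments made at the End-of-Treatment visit in the End of Treatment phase.

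Three protocol provisions govern what can fall inside the laboratory window:

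- Section 9.1.3 on visit timing: "The End-of-Treatment Visit is to occur within 30 days (+/- 7 days) after the last dose of study drug".
- Section 9.1.3 on the order of that visit and the next therapy: "Every effort should be made to conduct the End-of-Treatment Visit before the subject starts subsequent treatment".
- Section 8.3: "After treatment failure or relapse is established, subsequent therapy is permitted", at the investigator's discretion, with the start date to be recorded in the eCRF.

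**The concern.** The two safety rules point in opposite directions. The adverse-event rule takes the earlier of two dates, one of which is the start of the next therapy. The laboratory rule takes the later of two dates, neither of which is. The SAP gives no reason for the difference.

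A worst grade is a maximum, so one sample is enough to set it. Laboratory values in the shift table also carry no judgement of causality. For adverse events the relatedness assessment helps sort late events; for laboratory values a date rule is the only filter available.

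At stake is how the shift tables are read. A cytopenia that appears after a switch and is judged unrelated to study drug would be left out of the treatment-emergent adverse-event tables but could still count in the laboratory shift table of the same report.

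**Working it through.** There is no plan figure to reproduce. The check sets the windows side by side and follows the dates. Days are counted from the last dose of study medication.

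**End of each window**

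| Rule | Ends at | Cut at next therapy |
|---|---|---|
| Laboratory shift, SAP 6.8.2 | later of day 30 and the End-of-Treatment visit | none |
| Adverse events not judged related, SAP 5.15 | earlier of day 30 and start of next therapy | yes |
| Adverse events judged related, SAP 5.15 | no end date | none |
| Treatment Phase, SAP 5.3 | day 30 | none |
| ECG findings, SAP 6.8.3 | day 30 | none |
| Transfusions, SAP 6.7.3 | day 30 | none |

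**Length of the laboratory window.** The visit may be as late as 30 + 7 = 37 days and still be on schedule. The laboratory window then ends between day 30 and day 37. A visit later than that extends it further, because the later-of rule has no cap.

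**Days at issue.** Let the next therapy start on day d, with d below 30. The laboratory window then contains 30 − d days after the switch, or 37 − d if the visit falls on day 37. The documents do not give d, so these values are assumed:

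- d = 7: 30 − 7 = 23 to 37 − 7 = 30 days
- d = 14: 30 − 14 = 16 to 37 − 14 = 23 days
- d = 21: 30 − 21 = 9 to 37 − 21 = 16 days

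**Can a switch happen this early?** Yes. Protocol 8.3 permits it once failure or relapse is established and states no minimum interval after the last dose.

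**Can a sample fall after the switch?** Yes, by two routes. Protocol Table 1B schedules haematology and chemistry at the End-of-Treatment visit, and holding that visit before the next therapy is a best-effort request rather than a requirement. Protocol 9.9 also allows both panels to be repeated on clinical grounds.

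**Direction.** The maximum over a longer period is never below the maximum over a shorter period that it contains. Post-switch samples can leave the worst grade unchanged or raise it.

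**Does another passage supply the cut?** No. Neither SAP 5.3 nor the description of shift tables in Protocol 11.11 contains one.

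**The case against.** The strongest case is that the laboratory rule is not the odd one out. The Treatment Phase, ECG and transfusion windows also lack a cut; the adverse-event rule is the exception, and it is softened by readmitting related events. Laboratory values carry no attribution, so SAP 5.15 cannot simply be copied to them, and a fixed window is defensible. This stands as a reason for modesty. It does not explain why the two main toxicity summaries treat the same period differently.

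A cut also has a cost. The protocol describes decitabine as primarily myelosuppressive, and a nadir falling after an early switch may still belong to study drug. A hard cut would discard it and could understate the worst grade, again by arm if switching differs. This stands, and the fix must allow for it.

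The route is narrow. Table 1B schedules no laboratory tests in follow-up, the End-of-Treatment draw is the only scheduled one after treatment, and Table 1C, used during Amendment 6, lists none. The documents do not say whether unscheduled post-switch results reach the database. This stands, and it limits the size of the effect.

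A reader might infer that the table attributes toxicity from the next drug to study treatment. The documents do not support that: SAP 6.8.2 speaks of the worst grade during the study and assigns no cause. A post-switch abnormality could come from the new drug, a late study-drug effect or progressing leukaemia, so the tabulated grade is not shown to be wrong.

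**Conclusion.** The point holds as a minor one. The laboratory shift window admits post-switch samples, these can only raise the tabulated worst grade, and the inflation could differ by arm if the rate or timing of switching does. It affects a descriptive safety table only.

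The size cannot be derived from the documents, which give no switching rate, no timing and no frequency of post-switch sampling. A reader might multiply assumed rates. If 10% to 20% of subjects switch inside the window, 25% to 50% of these have a later sample in it, and 30% to 50% of those samples set a new worst grade, the products are 0.10 × 0.25 × 0.30 = 0.75% and 0.20 × 0.50 × 0.50 = 5%. All three inputs are guesses, and the upper end multiplies three maxima. For haematology the last input may be too high, since cytopenias are common in this disease and many subjects may already have reached a high grade. The range supports probably small and nothing more.

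A reader might also infer that SAP 5.15 closes the adverse-event window outright at the next therapy. It does not, because related events stay in.

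**What to change.** In SAP 6.8.2, end the shift window at the later of last dose + 30 days and the End-of-Treatment visit, or at the start of subsequent anticancer therapy if that is earlier. Keep samples drawn before the first dose of the new therapy, and state how a sample dated that same day is handled when no time is recorded. List values obtained after the switch separately, so that a delayed study-drug effect first seen then remains visible.

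This does not make the laboratory and adverse-event windows identical. For a subject with no new therapy and an End-of-Treatment visit on day 37, the laboratory window would still run 37 − 30 = 7 days beyond the cut-off for events not judged related, while related events would have no end date. The SAP should say so. If the sponsor prefers to keep the present window, a sentence giving the reason would suffice. The ECG and transfusion windows in SAP 6.8.3 and 6.7.3 deserve the same brief check.

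The cost is one clause, one date filter and one listing. No new data are needed, because the start date of subsequent therapy is already collected.
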